Results. Postoperative complication rates were (with NHS-PEG patch/without NHS-PEG patch): pancreatic fistula (A: 7.7%/7.7%; B: 0%/7.7%; C: 0%/15.5%); biliary fistula: 7.7%/15.4%; DGE: 7.7%/7.7%; hemorrhage: 7.7%/15.5%; exitus: 0%/7.7%; readmission: 7.7%/46%; mean stay: 21.3/26.1 days; other complications: 61.5%/46.2%.

Discussion. Sealing with NHS-PEG patch to prevent postoperative pancreatic fistula after DTM pancreaticojejunostomy can offer a new possibility to decrease POPF, with less fistula rate B and C, less hospital stay an less healthcare costs. Randomized controlled trials with larger number of patients should be performed to support this theory.

Therefore, we have design the following randomized controlled trial in order to validate our positive experience with Hemopatch in PD.

5. HYPOTHESIS / OBJECTIVE.

This unicentric, double-blind, randomized study investigates the efficacy and tolerance of Hemopatch in the prevention of POPF type B and C after a PD. The goal for Hemopatch is to reduce the risk of POPF type B and C from 30% to 15%.

6. STUDY DESIGN.

6.1. Type of study.

Unicentric, randomized, controlled, double-blind, prospective study with a parallel design of two groups. After giving informed consent, patients will not know to which group they have been assigned (reinforcement with Hemopatch or not). After the last follow-up visit on postoperative day 30, the patients can receive this information if they wish.

This study is also blind on the part of the observer; the final result will be determined by an independent observer, making this a double-blind study.

6.2. Primary objective and secondary objectives.

Primary endpoint: POPF type B and C, according to the definition of the ISGPF (Bassi, Surgery 2005), that is, the secretion of pancreatic fluid externalized through a drain or removed during a reoperation, independently of the color and / or appearance on day 3 or later, whose amylase is 3 times the values of serum amylase or collections (infected or not) detected by fistulography or other imaging techniques (computed tomography, ultrasound, magnetic resonance imaging). See attached table.

Grade	A	B	C
Clinical conditions	Well	Often well	Ill appearing / bad
Specific treatment*	No	Yes / no	Yes
US / CT (if obtained)	Negative	Negative / positive	Positive
Persistent drainage (after 3 weeks)**	No	Usually yes	Yes
Reoperation	No	No	Yes
Death related to POPF	No	No	Possibly yes
Signs of infections	No	Yes	Yes
Sepsis	No	No	Yes

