Readmission	No	Yes / no	Yes / no

US, Ultrasonography; CT, computed tomographic scan; POPF, postoperative pancreatic fistula.
*Partial (peripheral) or total parenteral nutrition, antibiotics, enteral nutrition, somatostatin analogue and/or minimal invasive drainage.
**With or without a drain in situ

Secondary endpoints:

- 1) Duration of postoperative hospital stay.
- 2) Duration of stay in intensive care unit.
- 3) Measurement of drainage debit.
- 4) Reinterventions including interventional radiology
- 5) Infection of the surgical site and / or dehiscence of the wound; complications in the deep organ space up to 30 days postoperatively.
- 6) Delayed gastric emptying.
- 7) Biliary fistula.
- 8) Postoperative hemorrhage.
- 9) Death, regardless of the cause.

6.3. Duration of the study.

The study will begin on February 1, 2018. Patients will be recruited at Miguel Servet University Hospital from January 1, 2018 to July 31, 2019. All patients randomly assigned will be followed for 30 days after surgery, or during the total stay in case it is longer than 30 days. They will also be evaluated in external consultations in the postoperative period for 3 months. A period of 4-6 months is considered to evaluate the data and the study will entail 2 years in total.

7. PATIENTS.

7.1. Criteria.

Despite improvements in morbidity after pancreatic resection, POPF after PD remains problematic. The incidence varies markedly in the literature, ranging from 0% to 64%, and 35% are clinically relevant. This great variability is attributed in part to the

indication and extension of the resection, as well as to the comorbidities of the patient. Other factors, such as age, male sex, obesity, prolonged operation time and a soft pancreas, as well as multivisceral resections increase the risk of fistula. The sequelae of pancreatic fistula after PD cover a broad spectrum. These patients often require visits to the emergency department, hospital readmissions, percutaneous drainage guided by interventional radiology, prolonged parenteral antibiotic therapy, radiological surveillance and numerous postoperative visits. The complications derived from the fistula double the cost of hospital treatment and dramatically increase the use of health resources.

7.2. Recruitment.

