- The investigator suspects a serious threat to the patient's well-being. Adverse events (any sign or symptom that affects the patient's well-being) and serious adverse events (life-threatening, prolongs hospital stay, results in persistent disability or leads to death during the observation period), as cardiopulmonary problems, in the gastrointestinal tract, anaphylactic shock or embolism will be recorded through daily postoperative visits until discharge and during the final visit on the 30th postoperative day. All adverse effects of clinical relevance and all serious adverse effects will be recorded in the case report form along with the degree of the complication (according to the Clavien-Dindo classification). The principal investigator must be informed within 24 hours about the serious adverse effects that occur during the hospital stay. The presence of a causal relationship between adverse effect or serious adverse effect and the intervention of the trial will be judged by the investigator. Serious adverse effects will be reported immediately (ie, within 5 days after recognition) by all investigators to the coordinating investigator. The coordinating researcher must inform the responsible ethics committee and the research sponsor. A list of all serious adverse effects must be compiled.

8. DATA.

8.1. Calculation of the sample size.

The sample size was calculated by comparing two proportions, with a level of statistical significance of 5% (alpha) and a statistical power of 80% (1-beta), and taking into account the preliminary data obtained regarding the rate of POPF in the two groups: 23% for the control group, and 7% for the Hemopatch group.

With these assumptions, it will take 57 patients to detect, with an 80% probability and a level of significance of 5%, a decrease of the POPF rate of 23% in the control group to 7% in the experimental group (Hemopatch). Considering an expected proportion of losses of 10%, the sample size will be 64 patients.

8.2. Randomization and groups.

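### The seriousness criteria in 7.7 leave out new or repeat hospitalisation, so a complication that is serious only because it causes readmission has no mandated report to the ethics committee

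*Combined protocol and SAP*

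**What the plan says.** Section 7.7 of the protocol separates adverse events from "serious adverse events (life-threatening, prolongs hospital stay, results in persistent disability or leads to death during the observation period". Both kinds "will be recorded through daily postoperative visits until discharge and during the final visit on the 30th postoperative day".

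Three duties are tied to seriousness:

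- Early notice: "The principal investigator must be informed within 24 hours about the serious adverse effects that occur during the hospital stay".
- Onward reporting: "Serious adverse effects will be reported immediately (ie, within 5 days after recognition) by all investigators to the coordinating investigator". The next sentence continues: "The coordinating researcher must inform the responsible ethics committee and the research sponsor".
- Compilation: "A list of all serious adverse effects must be compiled".

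Non-serious events of clinical relevance go into the case report form with a Clavien-Dindo grade.

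Two other routes do not depend on seriousness. Under Materials in 7.4, undesirable effects attributed to Hemopatch go at once to the coordinator and the manufacturer. Under section 9, a monitoring team receives all patient data and stays in contact with the main coordinator.

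Readmission appears in several other places. Section 7.1 says of fistula after this operation: "These patients often require visits to the emergency department, hospital readmissions, percutaneous drainage guided by interventional radiology". The fistula grading table in 6.2 allows readmission for grades B and C. Section 8.3 collects it as re-entry. The preliminary case series reports, patch first and no patch second, "readmission: 7.7%/46" percent.

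**The concern.** The four criteria form a closed list. The one that concerns hospital care refers to lengthening a stay, which in its ordinary sense means a stay already in progress. A patient who goes home and is admitted again with a complication meets that criterion only on a generous reading.

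Seriousness can then turn on the date of discharge instead of on what happened to the patient. Section 7.6 describes grade B fistula as symptomatic but clinically stable, possibly needing percutaneous drainage. If it appears on the ward and delays discharge, it is serious. If it appears at home and brings the patient back, it may be life-threatening, disabling or fatal in no respect, and so be non-serious. Yet it is a primary-endpoint event in both cases.

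Safety and tolerance is the trial's stated secondary objective, and section 10 presents fewer readmissions as an expected benefit. A serious-event list that can omit events leading to readmission is a weak basis for oversight by the ethics committee and sponsor.

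**Working it through.** **1. Reproduce the pilot counts.** The case series had 26 operations, 13 with the patch and 13 without.

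- Without patch: 6/13 = 46.15% (stated 46%).
- With patch: 1/13 = 7.69% (stated 7.7%).

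Both figures reproduce.

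**2. Precision of those counts.**

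- Exact (Clopper-Pearson) 95% intervals: 19.2% to 74.9% for 6/13, and 0.2% to 36.0% for 1/13.
- Fisher's exact test with 7 readmissions among 26 patients: P(1 in patch arm) = C(13,1) × C(13,6) / C(26,7) = 13 × 1,716 / 657,800 = 0.0339. P(0 in patch arm) = 1,716 / 657,800 = 0.0026. Their sum is 0.0365; doubling for the symmetric other tail gives p = 0.073.

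**3. Scale to the trial.** This assumes that pilot rates hold with 32 patients per arm.

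| Arm | Calculation | Expected readmitted | 95% range from the pilot interval |
|---|---|---|---|
| Without patch | 32 × 6/13 | 14.8 | 6 to 24 |
| With patch | 32 × 1/13 | 2.5 | 0 to 12 |
| Total | | 17.2 of 64 | |

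**4. From readmissions to events missed.** About 17 is the ceiling at pilot rates. It requires every readmission to fall inside the recording window and none to qualify as serious on another criterion. The floor is 0. The documents give no causes, severity or timing for pilot readmissions, so nothing narrows the range exactly.

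**5. The recording window.** Section 7.7 places its last safety recording at the day-30 visit. Pilot mean stay was 21.3 days with the patch and 26.1 without. If those are index stays, the average time at risk between discharge and day 30 is 30 − 21.3 = 8.7 days and 30 − 26.1 = 3.9 days. Means hide variation, but some pilot readmissions may lie beyond day 30, which pulls the number below 17.

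**6. Where a readmission-only event goes under the current text.**

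| Route | Covers it? | Reaches the ethics committee by rule? |
|---|---|---|
| Case report form (7.7) | Yes, if clinically relevant | No |
| Serious-event list and 5-day report (7.7) | No | Not triggered |
| Hemopatch-effect notice (7.4, Materials) | Only if attributed to the patch, so never for controls | No; coordinator and manufacturer only |
| Monitoring team (9) | Yes | No such duty stated |

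**The case against.** The strongest defence is that little is hidden. The monitoring team sees all data without a seriousness filter and has a standing link to the coordinator. Patch-related effects are notified faster than the 5-day rule requires. Reinterventions and deep organ-space complications are secondary endpoints, and readmission and Clavien-Dindo grade are collected in both arms. All of this stands, and it limits the consequences. It does not supply an individual report to the ethics committee, and the patch-effect route cannot serve the control arm.

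It can also be argued that lengthening the hospital stay was meant to include a second admission. If so, one clause would settle it; the present text does not say so.

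Four stronger readings are tempting, and the documents do not support them:

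- *A reader might infer that most complications after discharge escape the serious-event rules.* No figure supports this. Those that are life-threatening, disabling or fatal within the observation period still qualify, and the range in the working starts at 0.
- *A reader might infer that readmission was the commonest problem among pilot controls.* It ties at 6/13 with the mixed category of other complications, on only 13 patients.
- *A reader might infer that such events never reach the coordinator or sponsor.* Sections 7.4 and 9 give routes to the coordinator. The patch-effect route goes to the manufacturer, and 3.1 names Baxter, the source of the Hemopatch instructions in the reference list, under Sponsor.
- *A reader might infer that the comparison of serious events between arms is distorted.* Section 8.5 plans no such comparison, and the pilot difference in readmission is itself imprecise (p = 0.073).

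**Conclusion.** The omission is real but narrow. Section 7.7 states a closed rule under which a complication that leads only to readmission is non-serious, while the same complication before discharge is serious if it lengthens the stay. What is lost is a place on the serious-event list, the individual report to the ethics committee, and the report to the sponsor outside the patch-effect route. Data capture and visibility to the monitoring team are not lost.

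The size is unknown: 0 to about 17 of 64 patients at pilot rates, and probably well below the upper end. This rests on 13 patients per pilot group, on pilot rates carrying over to the trial, and on reading the hospital-stay criterion as referring to a current admission. Sample size and the primary analysis are untouched. The point is a cheap improvement to safety reporting.

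**What to change.** In 7.7, replace the hospital-stay criterion with: *requires or prolongs hospitalisation (including unplanned readmission)*. Apply it identically in both arms, and include events that qualify this way in the compiled list.

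In the same amendment, reconcile the reporting routes in 7.4 (Materials), 7.7 and 9. State who informs the ethics committee and sponsor about an individual event that comes to light after discharge. State also whether the 24-hour notice to the principal investigator, now limited to the hospital stay, covers a readmission.

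Making every reoperation or radiological reintervention serious by rule is optional. These are already captured as an endpoint, and closing the gap does not require it.

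Cost: one sentence for the definition, a short clarification of routes, and somewhat more serious-event reports. No new data are needed, since 8.3 already collects readmission.

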Objetives	Primary objective: 
• To demonstrate the effectiveness of Hemopatch in the prevention of postoperative pancreatic fistula after PD with duct-to-mucosa reconstruction against ductomucosal reconstruction without Hemopatch Secondary objectives: 
• To assess the safety and tolerance of Hemopatch in patients undergoing PD
Interventions	Performing duct-to-mucosa anastomosis with or without Hemopatch reinforcement after PD
Inclusion and exclusion criteria	Inclusion criteria: patients submitted to PD by laparoscopic or open approach for benign / malignant tumors or chronic pancreatitis; ASA < 4; men and women ≥ 18 and ≤ 80 years of age. Exclusion criteria: patients under 18 and over 80 years old; ASA score ≥ 4 ; subjected to multivisceral resections different from PD; patients with acute necrotizing pancreatitis; immunosuppressed patients; patients who have not signed the informed consent; patient with contraindication of PD performance
Results	Primary point: Type B and C postoperative pancreatic fistula defined according to the criteria of the International Study Group on Pancreatic Fistula (ISGPF) Secondary endpoints: 
1) Duration of postoperative hospital stay.2) Length of stay in intensive care unit.3) Measurement of drainage debit.4) Reinterventions including interventional radiology.5) Infection of the surgical site and / or dehiscence of the

Study protocol - Use of Hemopatch as a sealant in pancreaticojejunostomy after PD.
Version 2.0.

	wound; complications in the deep organ space up to 30 days postoperatively. 6) Delayed gastric emptying. 7) Biliary fistula. 8) Postoperative hemorrhage. 9) Death, regardless of the cause.
Type of study	Prospective randomized double blind unicentric clinical trial

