All patients undergoing PD, either by laparotomy or laparoscopy, are potential participants. Their diagnoses include chronic pancreatitis, benign (for example, cystadenoma) or malignant tumors (adenocarcinoma, NET, metastasis, etc.). They will be invited to participate in the study and will be informed of the possible advantages and disadvantages. The randomization process will begin for any patient who agrees to participate after informed consent.

7.3. Inclusion and exclusion criteria.

Inclusion criteria: patients submitted to PD by laparoscopic or open approach for benign / malignant tumor or chronic pancreatitis; ASA < 4; men and women ≥ 18 and ≤ 80 years of age.

Exclusion criteria: patients under 18 and over 80 years old; ASA score ≥ 4 ; subjected to multivisceral resections different from PD; patients with acute necrotizing pancreatitis; immunosuppressed patients; patients who have not signed the informed consent; patient with a contraindication to PD.

7.4. Intervention techniques and materials.

The indications for performing a PD are multiple. The type of reconstruction to be performed will depend basically on the characteristics of the pancreatic remnant. However, in our center, the usual reconstruction technique is the duct-to-mucosa type pancreaticojejunostomy.

Depending on the randomization, patients will be operated as follows:

- 1) Basic treatment: standard duct-to-mucosa pancreaticojejunostomy.
- 2) Basic treatment plus Hemopatch: standard pancreaticojejunostomy + reinforcement with 2 Hemopatch of 90 x 45 mm, one on each side (lower and upper) as a "scarf".

In both groups, passive external drainage is mandatory for a period of 7 days with drainage placed next to the anastomosis but not in contact with it. The drain can be a Penrose drain, a Jackson-Pratt drain or Blake without active suction. Suction drains are not allowed.

Adjvant procedures

Wrapping, sealing with fibrin or serous patch with another adjacent organ are not acceptable. No resection of adjacent hollow organ is allowed (excepting those included in the standard DPC).

Materials

Hemopatch is a hemostatic-sealant made of collagen that resorbs in 6-8 weeks. The active side is covered with a polyethylene glycol film for better adhesion.

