Hemopatch is a medical product with CE certificate (Annex IV - excluding section 4 of Council Directive 93/42 / EEC on medical devices) used for hemostasis. It is not designed for use with heavy or pulsatile bleeding or with acute infections. It also has indication of sealant from March 2016. Hemopatch should not be used intravascularly. It also can not be used for patients who are allergic to any of the materials listed by the manufacturer. The only known side effect is the rare case when Hemopatch can not achieve the desired hemostasis. With documentation of the patient's clinical course, regular blood tests and imaging tests when necessary, any undesirable effects derived from the use of Hemopatch must be diagnosed in a timely manner and appropriate measures will be taken, the coordinator will be immediately informed, the person in charge of the control of the test and, likewise, an immediate communication of the adverse effect to the manufacturer will be sent.

7.5. Postoperative period.

In the postoperative period, the parameters of inflammation, body temperature, visual analog pain scale (VAS), drainage debit and its amylase / lipase content will be documented. To facilitate the healing process, drainage should be left in place for at least 7 days. In the absence of evidence of fistula, the drainage may be withdrawn. If the 7th postoperative day there is evidence of pancreatic fistula according to the ISGPF criteria, the drainage will be maintained until the resolution of the same.

All patients are advised to follow the instructions given at discharge. If there is any reason for the alarm (pain, fever, tachycardia) the patient should go to the hospital where he was treated at any time. A final visit will be scheduled on postoperative day 30 to evaluate any collection of intra-abdominal fluids through the clinical examination and the performance of an ultrasound or CT scan (as is done routinely).

7.6. Complications / failure of the intervention.

POPF are defined according to the definition published in 2005 by the International Study Group on Pancreatic Fistula (ISGPF), which is based on the concentration of amylase in the drainage fluid. A POPF is defined when the concentration of amylase in the drainage fluid is three or more times greater than in serum from the third postoperative day.

Pancreatic fistulas are classified in 3 grades, from A to C:

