All study personnel must sign a confidentiality agreement that covers all aspects of the study and its data. The study directors will take particular responsibility for the security of the data, the documents of origin and the information about the patients.

The coordinator of the main study is also responsible for continuing education in Good Clinical Practices (GCP) in accordance with the Declaration of Helsinki.

8.5. Statistical methods and data analysis.

For the evaluation of the primary objective, patients will be dichotomized by the presence or absence of the sealant reinforcement. In addition, patients will be classified by the type of pancreatic fistula defined according to the ISGPF. Next, a contingency table will be created to calculate the positive predictive value, specificity, sensitivity and the c-index. The association between sealant reinforcement and pancreatic fistula rate will be expressed as an odds ratio calculated by logistic regression models with the appropriate covariates. The strength of association between the categorical variables will be tested with a chi-square test with the Yate correction.

Secondary objectives will be analyzed descriptively by tabulation. Chi-square tests will be used to test associations between categorical variables, while Student's t-test or Mann-Whitney U-test will be used to compare normal or non-normal data, respectively. Time-dependent variables will be tested by Kaplan-Meier analysis and Cox regression. The statistical analysis will be carried out with R.

9. PATIENT SAFETY.

A monitoring team will receive all patient data electronically including expected and unexpected events and side effects for all patients in the study. All patient data are analyzed to detect any unusual pattern. There will be permanent contact with the main coordinator of the study and will meet face to face three times a year to evaluate the course of the study based on the data collected.

10. IMPACT ON CLINICAL PRACTICE.

Hemopatch is expected to reduce the risk of postoperative type B and C pancreatic fistula from 30% to 15%, so that the number of patients currently requiring readmission with possible surgeries and interventional radiological procedures is halved. This implies not only clinical but also economic advantages, since a pancreatic fistula can double the cost of hospital treatment.

11. ETHICS AND LEGAL REQUIREMENTS.

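### For patients discharged by day 30, scheduled adverse-event recording stops 12 to 26 days before the stated end of patch resorption, although outpatient review continues for 3 months

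*Combined protocol and SAP*

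**What the plan says.** The synopsis lists one secondary objective: "To assess the safety and tolerance of Hemopatch in patients undergoing PD".

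Section 7.7 fixes when adverse and serious adverse events are captured: they "will be recorded through daily postoperative visits until discharge and during the final visit on the 30th postoperative day".

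On the device, section 7.4 states: "Hemopatch is a hemostatic-sealant made of collagen that resorbs in 6-8 weeks".

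On follow-up, section 6.3 says that randomized patients "will be followed for 30 days after surgery, or during the total stay in case it is longer than 30 days", and then adds: "They will also be evaluated in external consultations in the postoperative period for 3 months". It gives neither dates nor content for these consultations.

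Two other sections treat day 30 as the end. Section 7.5 says: "A final visit will be scheduled on postoperative day 30 to evaluate any collection of intra-abdominal fluids". Section 6.1 ties disclosure of allocation to the same visit: "After the last follow-up visit on postoperative day 30, the patients can receive this information if they wish".

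Section 9 adds: "A monitoring team will receive all patient data electronically including expected and unexpected events and side effects for all patients in the study". It states no period over which those data are gathered.

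**The concern.** The trial sets out to assess the safety of an absorbable patch, yet for a patient who goes home within a month the scheduled safety record closes while the patch, on the plan's own figure, is still being resorbed. The same patient is then seen by the team for roughly two more months with no instruction to record adverse events.

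What is at stake is the scope of the safety conclusion. An event in week 6 could be known to the clinicians and still be missing from the comparison of arms, or be present in one arm only because somebody suspected the patch. A statement that the patch was well tolerated would then rest on 30 days of scheduled observation without saying so.

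The length of recording also depends on length of stay, because inpatients are recorded until discharge. If stay differs between arms, so does observation time. The documents do not allow the size of that effect to be estimated.

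**Working it through.** The plan gives no figure of its own on this point, so there is none to reproduce. The check is day arithmetic on the stated windows.

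**Inputs**
- Last scheduled recording point for a patient already discharged: day 30 (section 7.7).
- Resorption time R: 6-8 weeks, that is 6 × 7 = 42 to 8 × 7 = 56 days (section 7.4).
- Outpatient review: 3 months, taken here as about 90 days from surgery. This is an assumption, as section 6.3 does not define the starting point.
- Pilot mean stay: 21.3 days with the patch and 26.1 days without, 13 patients per group (case series in the background).

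**Patient discharged by day 30**
- Uncovered days = R − 30: 42 − 30 = 12, and 56 − 30 = 26.
- Uncovered share = (R − 30)/R: 12/42 = 28.6%, and 26/56 = 46.4%.
- Covered share = 30/R: 30/42 = 71.4%, and 30/56 = 53.6%.
- Outpatient period without scheduled recording: 90 − 30 = 60 days.

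**Patient discharged on day D, after day 30**
- Recording continues to discharge, so uncovered days = max(0, R − D). For illustration, D = 40 leaves 42 − 40 = 2 to 56 − 40 = 16 days. From D = 56 nothing is uncovered.

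**How many patients are affected**
- Both pilot means lie below 30 days. The distribution of stay is not given. If it is right-skewed, as length of stay usually is, more than half of patients leave before the mean. Most patients are therefore probably affected, but no percentage can be given.

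**Does another clause close the gap?**
- Section 7.4 requires prompt diagnosis and notification of undesirable effects that derive from the patch. It has no day-30 limit, but it has no counterpart in the control arm.
- Section 7.7 has a 24-hour rule confined to the hospital stay, and a 5-day rule for serious events that starts when the event is recognised. The latter has no stated end, but it sets no occasion on which patients are asked.
- Section 8.3 lists readmission, reinterventions and graded complications as data to collect, and section 8.4 puts adverse events on the data sheet. Neither states a period.
- The monitoring team in section 9 can review only what has been collected.

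None of these sets up scheduled collection in both arms after day 30.

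**After the change**
- Recording to about day 90 covers the whole resorption period with 90 − 56 = 34 to 90 − 42 = 48 days to spare.

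**The case against.** The strongest reply is that the documents are silent about late events and do not exclude them. A readmission or suspected device reaction in week 6 could reach the trial through the clauses on serious events, patch-related effects or readmission. That stands. A reader might infer that events after day 30 cannot enter the data, and the text does not support this. What it lacks is systematic collection in both arms, which a comparison needs.

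A reader might also apply the gap to every treated patient. That is wrong, because patients still in hospital after day 30 are recorded until discharge.

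Nor do the documents show that resorption causes late harm. Section 7.4 names a single known side effect, failure to achieve hemostasis, and section 7.5 already schedules examination and imaging at day 30. The 29% to 46% is a share of calendar days. It is not a share of risk, since a resorbing patch is not a constant exposure.

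Two further points stand in part. With 32 patients per arm, late data say little about rare events: zero events in 32 leaves a one-sided 95% upper bound of 1 − 0.05^(1/32) = 8.9%. That limits what can be learned, but it applies equally to the first 30 days and is no reason to leave later events unrecorded at contacts already planned. And a 30-day window is openly stated and matches the window for surgical-site complications among the secondary endpoints. It is a defensible choice if the safety conclusion is limited to it.

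Finally, section 6.3 does not specify a visit at month 3, and patients may be told their allocation after day 30. Both bear on the remedy and are dealt with there.

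**Conclusion.** The point holds for patients discharged by day 30. For them, 12 to 26 calendar days of the stated resorption period (29% to 46%), and about 60 of some 90 days of outpatient review, have no scheduled two-arm adverse-event collection. This rests on reading section 7.7 as the definition of scheduled recording, on the 6-8 weeks of section 7.4, and on 3 months being about 90 days from surgery. That most patients are affected is an inference from two small pilot means.

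It is an ascertainment gap for the safety objective. The documents do not show that harm has been or will be missed, and the analysis of the primary endpoint is unaffected. The change is worth making because it is cheap, not because the trial fails without it.

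**What to change.** 1. In section 7.7, record adverse and serious adverse events in both arms, with the same form and questions, at the outpatient consultations of section 6.3, to about 3 months. Fix the timing of the last consultation, which section 6.3 leaves open.
2. In section 8.5, tabulate by arm the events to day 30 and, separately, those from day 31 to 3 months.
3. Reconcile the day-30 final visit in sections 6.1, 7.5 and 7.7 with section 6.3, and state what is collected at the later consultations.
4. In section 6.1, either move disclosure of allocation to the end of safety follow-up or label reports after day 30 as possibly unblinded on the patient's side.

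The cost is one more case report form page, a fixed date for the last consultation, a later disclosure or a caveat on late reports, and closure of the safety data about two months after the last patient's day-30 visit. If the sponsor keeps the present window, the safety conclusion should be expressly limited to 30 days or the hospital stay, whichever is longer.
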